**Step 2**

R code similar to the code below can be used to determine the AV delay (best AV delay) which leads to the maximum predicted response based on the fitted model for each patient.

[REDACTED]

[REDACTED]

**Step 3**

Within SAS, PROC GLM can be used to determine the standard error of the predicted change dP/dt max at best AV delay δ, i.e., the standard error of the predicted maximum change dP/dt max. We would like to take this standard error into account since subjects with less precise estimates of maximum LV dP/dt max should have less influence in the following comparison between configurations. [REDACTED]

[REDACTED]

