Endpoint for the primary objective 1, primary objective 2 and secondary objective 1 will be % change LV dP/dt max from baseline. This percentage change is calculated as $([\text{median dP/dt max during pacing On}] - [\text{median baseline dP/dt max during pacing Off}]) / [\text{median dP/dt max during pacing Off}]$. This endpoint will be used primarily to evaluate the hypothesis of objective 1, primary objective 2 and secondary objective 1. Other endpoints, e.g., blood pressures, might be included in an exploratory secondary analysis for these objectives.

H.1.1 Primary objective 1

Compare the hemodynamic response of a MultiSpot-SYN Left Ventricular pacing configuration (simultaneous LV pacing) to a single spot LV pacing configuration in patients undergoing a research study, an EP exploratory procedure or CRT implant using the contractility parameter positive LV dP/dt max.

It is hypothesized that MultiSpot SYN (pacing on all 3 LV electrodes simultaneously) is superior to conventional BiV pacing (i.e. using only the basal LV electrode).

The null and alternative hypotheses are:

$$H_0: \Delta_{\text{MultiSpot SYN}} - \Delta_{\text{BiV}} = 0\%$$

$$H_1: \Delta_{\text{MultiSpot SYN}} - \Delta_{\text{BiV}} \neq 0\%,$$

where Δ indicates percentage change from baseline for the respective pacing configuration.

For each patient, a regression analysis will be performed to model % change LV dP/dt max dependent on configuration and AV delay. Based on the fitted model for each patient, the best AV delay for each configuration will be determined together with the predicted % change at this best AV delay. This best AV delay may differ from the optimal AV delay determined by the CardioSync formula. Paired two-sided t-tests will be used to evaluate whether there is a statistical significant difference between MultiSpot-SYN and standard BiV pacing. Instead of paired t-tests, a Wilcoxon signed rank test might be performed if normality is violated.

H.1.2 Primary objective 2

Compare the hemodynamic response of a MultiSpot-SEQ Left Ventricular pacing configuration (sequential LV pacing) to a single spot LV pacing configuration in patients undergoing a research study, an EP exploratory procedure or CRT implant using the contractility parameter positive LV dP/dt max.

It is hypothesized that MultiSpot SEQ (pacing on 3 LV electrodes activated sequentially from apex to mid and then to base) is superior to conventional BiV pacing (i.e. using only the basal LV electrode).

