**6. Determination of Sample Size****6.1. Primary Objective #1**

The sample size calculation is based on the primary objective 1 and the primary endpoint, i.e., % change LV dP/dt max from baseline (AAI setting). This study is powered to show superiority of MultiSpot SYN pacing to BiV pacing (standard CRT) for the primary endpoint % change + LV dP/dt max from baseline (AAI pacing). Assuming an expected difference in % change between MultiSpot and BiV pacing of 3.5% and standard deviation of 7%, 34 patients would have 80% power to demonstrate superiority. The total sample size is increased to 40 patients to accommodate for data collection problems during the EP

procedure. The following null-hypothesis  $H_0$  and alternative hypothesis  $H_1$  will be evaluated at a significance level of 0.05:

$$H_0: \Delta_{\text{MultiSpot SYN}} - \Delta_{\text{BiV}} = 0\%$$

$$H_1: \Delta_{\text{MultiSpot SYN}} - \Delta_{\text{BiV}} \neq 0\%,$$

where  $\Delta$  indicates percentage change from baseline for the corresponding configuration. Previous literature and results from the iSPOT study suggests that the average difference in percentage change between MultiSpot SYN and BiV pacing is 2.5% in a normal HF population (iSPOT study, Sohal, et al., 2015; Thibault, et al., 2013). For the standard deviation of the difference in % change between MultiSpot and BiV pacing we assume 7% based on previous literature and the iSPOT study.

Not much literature is available for the difference in % change between MultiSpot and BiV pacing for the study population targeted in this study. This study selects "difficult" CRT patients in order to adequately address the potential benefit of MultiSpot Pacing in this patient population. The term "difficult" represent those patients with an increased likelihood of non-response to conventional cardiac resynchronization therapy (e.g. ischemic patients or non-LBBB left ventricular dyssynchrony patients). Based on few small subgroup analyses (iSPOT study, Sohal, et al., 2015), we expect that the difference in % change between MultiSpot SYN and BiV pacing will be slightly higher in the targeted study population, namely 3.5%. The sample size calculation is based on this difference of 3.5% and a standard deviation of 7%.

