## 7.2. General Methodology

Data summaries for categorical data will be summarized as count, e.g., number of patients, and/or number of events, and a percentage relative to the total number of patients/events. The denominator will be explicitly identified when not clear from the context. Continuous variables will be represented by mean and standard deviation, except when the distribution of the variable is highly skewed in which case median and quartiles will be reported.

P-values for hypothesis testing will be evaluated based on two-sided testing using significance level of 0.05 except for the non-inferiority testing (secondary objective 1) which is evaluated using one sided testing and a significance level of 0.025. Confidence intervals will be reported as two-sided 95% confidence intervals.

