### 7.9.1.3. Analysis Methods

#### A. Statistical Methodology

The following steps will be applied for analysis.

1. Regression model per patient
2. Use the parameter estimates from regression model to obtain predicted maximum response and corresponding best AV delay per configuration
3. Use PROC GLM to obtain the standard error of the predicted maximum response
4. Perform weighted t-test for comparison between configurations

#### Step 1

For each patient, a regression analysis will be performed to model % change LV dP/dt max dependent on configuration and AV delay. The model will include effects for configuration, for AV delay up to a quadratic order, and interaction effects. AV delay will have values 0, -30, +30, -60, 60 ms to indicate the difference between the applied AV delay and the optimal AV delay based on the Cardio Sync formula. AV delay will be treated as a continuous variable. The following regression model will be applied for each subject:

$$\begin{aligned} \% \text{ change} = & \beta_1 * \text{Configuration}_1 + \beta_2 * \text{Configuration}_2 + \beta_3 * \text{Configuration}_3 + \beta_4 * \text{Configuration}_4 + \\ & \beta_5 * \text{Configuration}_5 + \beta_6 * \text{AVdelay} + \beta_7 * \text{AVdelay}^2 + \beta_8 * \text{Configuration}_1 * \text{AVdelay} + \beta_9 * \\ & \text{Configuration}_2 * \text{AVdelay} + \beta_{10} * \text{Configuration}_3 * \text{AVdelay} + \beta_{11} * \text{Configuration}_4 * \text{AVdelay} + \beta_{12} * \end{aligned}$$

$$\text{Configuration}_5 * \text{AVdelay} + \beta_{13} * \text{Configuration}_1 * \text{AVdelay}^2 + \beta_{14} * \text{Configuration}_2 * \text{AVdelay}^2 + \beta_{15} * \text{Configuration}_3 * \text{AVdelay}^2 + \beta_{16} * \text{Configuration}_4 * \text{AVdelay}^2 + \beta_{17} * \text{Configuration}_5 * \text{AVdelay}^2 + \varepsilon.$$

Configurationi is 1 if at time point t pacing configuration i is performed and 0 otherwise. The error is denoted by ε. For ease of interpretation, no intercept is included in the model such that the estimate βi correspond to the estimated mean % change during configuration i. Alternatively, one could include an intercept which would then model a reference configuration.

[REDACTED]

[REDACTED]

[REDACTED]

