### 7.9.3.3. Analysis Methods

#### A. Statistical Methodology

Statistical analysis will use the methods described for the primary objective 1, with single spot LV pacing configuration (standard BiV) replaced by MultiSpot-SEQ LV pacing.

Inferiority testing will be performed one-sided at a significance level of 0.025. Non-inferiority of MultiSpot SEQ to MultiSpot SYN will be declared if the lower limit of a two-sided 95% confidence interval for the mean difference between MultiSpot SEQ and SYN does not fall below -3%. Superiority testing will be performed two-sided at a significance level of 0.05.

Results for non-inferiority testing will be summarized in a table similar to the table below:

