### **7.12. Changes to Planned Analysis**

This Statistical Analysis Plan does not deviate from the planned statistical analysis in the CIP. The analysis cohort has been described in the CIP as follows: "The Analysis Population is defined as patients, who are enrolled, have no inclusion or exclusion criteria violation regarding the most important criteria, i.e., inclusion criteria 1 and 2 and exclusion criterion 3, and for whom the EP procedure could be completed successfully." This definition has been clarified in the SAP to the following definition: "The Analysis Population is defined as patients who are enrolled, have no inclusion or exclusion criteria violation regarding the most important criteria, i.e., inclusion criteria 1 and 2 and exclusion criterion 3, and have less than 3 months between MRI and EP visit."

Any change to the data analysis methods described in the Clinical Investigational Plan will require an amendment only if it changes an objective of the Clinical Investigational Plan. Any other change to the data analysis methods described in the Clinical Investigational Plan and this Statistical Analysis Plan, and the justification for making the change, will be described in the clinical study report. Additional exploratory analyses of the data will be conducted as deemed appropriate.

---

**8.** [REDACTED]

[REDACTED]

[REDACTED]

[REDACTED]

[REDACTED]

[REDACTED]	[REDACTED]	[REDACTED]
[REDACTED]	[REDACTED]	[REDACTED]
[REDACTED]	[REDACTED]	[REDACTED]
[REDACTED]	[REDACTED]	[REDACTED]
[REDACTED]	[REDACTED]	[REDACTED]
[REDACTED]	[REDACTED]	[REDACTED]
[REDACTED]	[REDACTED]	[REDACTED]

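### The weighted t-test can run above its stated 0.05 and 0.025 levels if, as the visible SAP text suggests, its weights rest on within-patient fit error alone

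*SAP*

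**What the plan says.** SAP 7.9.1.3 lists four steps. Step 1 fits one regression per patient of % change in LV dP/dt max on configuration and AV delay (quadratic). Step 2 finds the best AV delay and the predicted maximum for each configuration. Step 3 takes the standard error of that predicted maximum from PROC GLM, with the reason that "subjects with less precise estimates of maximum LV dP/dt max should have less influence in the following comparison between configurations". Step 4 reads "Perform weighted t-test for comparison between configurations". The rest of Step 3 is redacted, and the text of Step 4 was not in the copy available for this review, so the weight formula cannot be read. None of the four listed steps names an estimate of between-patient variance.

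The other objectives inherit the method. SAP 7.9.2.3 and 7.9.3.3 both say "Statistical analysis will use the methods described for the primary objective 1". The test therefore feeds Tables 9 and 11 (primary objectives) and Tables 12 and 13 (SEQ against SYN, with a margin of -3%).

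Protocol H.1.1 names a different test: "Paired two-sided t-tests will be used to evaluate whether there is a statistical significant difference", with a Wilcoxon signed rank test as fallback and no weights. SAP 7.12 nevertheless states: "This Statistical Analysis Plan does not deviate from the planned statistical analysis in the CIP".

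On error rates, SAP 7.2 says "P-values for hypothesis testing will be evaluated based on two-sided testing using significance level of 0.05 except for the non-inferiority testing", which is one-sided at 0.025. On variability, SAP 6.1 says of the SD of the difference "we assume 7% based on previous literature and the iSPOT study". Neither document splits that 7% into a between-patient part and a fit-error part.

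**The concern.** A weighted t-test is valid when each patient's difference has a variance proportional to 1/weight. Here patient i's difference has variance tau² + SE_i², where tau² is the true between-patient variance of the difference and SE_i² is the fit error. If the weights follow SE_i² alone while tau² is material, the true variances are more alike than the weights imply. The weighted mean then leans on a few patients, and the usual formula does not register the loss of effective sample size.

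At stake are both primary comparisons and the non-inferiority interval. Superiority, or non-inferiority at -3%, could be declared more often than the stated levels allow, and the reported 95% intervals could cover less than 95%.

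**Working it through.** **1. The plan's own figures.** An ordinary unweighted paired t-test (noncentral t) gives:

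- SYN against BiV, difference 3.5, SD 7, two-sided 0.05: n = 34, power 80.8% (SAP 6.1: 34 patients, 80%).
- SEQ against BiV, difference 4, SD 7: power 89.9% at n = 34 (SAP 6.2: 90%).
- Non-inferiority, margin -3, true difference +0.5, so distance 3.5, one-sided 0.025: power 80.8% at n = 34 (SAP 6.3: 80%).

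All three reproduce, and all three describe the unweighted test.

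**2. Could between-patient variance be material?** For a quadratic on AV offsets -60, -30, 0, 30 and 60 ms (SAP Step 1), the variance of the fitted value, relative to the variance of the mean of the repeats at one delay, is 17/35 = 0.486 at 0, 13/35 = 0.371 at ±30 and 31/35 = 0.886 at ±60. SAP 7.9.1.2 gives eight % changes per combination. With residual SD s for one % change (not in the documents, so assumed), the fit SE of a paired difference is:

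- best delay at 0 in both configurations: s × √(2 × 0.486/8) = 0.35s
- best delay at ±60 in both: s × √(2 × 0.886/8) = 0.47s

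As a share of 7² = 49, fit error is 2 to 4% at s = 3, 6 to 11% at s = 5 and 16 to 29% at s = 8. It reaches half only at s of about 10.5 to 14, or about 7.4 to 10 if only four of the eight values are independent. Material between-patient variance is therefore plausible over a wide range of s.

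**3. The mechanism.** The standard weighted test estimates the variance of its mean as Σw(d - mean)² / [(n - 1)Σw]. When true variances are about equal, the ratio of true to estimated variance is (n - 1)/(n_eff - 1), with n_eff = (Σw)²/Σw². For example, n_eff = 20.8 gives 33/19.8 = 1.67, so the SE should be about 1.29 times the reported one.

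**4. Size by share of between-patient variance.** Simulation of 100,000 trials, n = 34, mean variance 49, weights 1/SE², best delay spread evenly over the five offsets. Entries are two-sided / one-sided type I error, by log-SD of the residual SD across patients (assumed).

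| Between-patient share | log-SD 0 | 0.15 | 0.25 | 0.35 | 0.5 |
|---|---|---|---|---|---|
| 95% | 5.9 / 3.0% | 6.7 / 3.4% | 9.0 / 4.5% | 12.6 / 6.3% | 20.8 / 10.3% |
| 50% | 5.5 / 2.8% | 6.0 / 2.9% | 7.4 / 3.7% | 10.0 / 5.0% | 17.3 / 8.7% |
| 0% | 5.0 / 2.5% | 5.0 / 2.5% | 5.0 / 2.5% | 5.0 / 2.5% | 4.9 / 2.5% |

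At 95% and log-SD 0.35, n_eff averages 20.8; the true SE is 1.53 and the mean estimated SE is 1.16.

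**5. Size by residual SD.** Residual SD 3, 5 or 8 points, four or eight independent repeats, total SD 7:

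| log-SD | 1/SE², two-sided | 1/SE², one-sided | 1/SE, two-sided |
|---|---|---|---|
| 0 | about 6% | about 3% | about 5% |
| 0.2 | 7–8% | about 4% | 5–6% |
| 0.3 | 9–11% | 4–5% | 5–6% |
| 0.4 | 12–15% | 6–8% | 5–7% |
| 0.5 | 15–21% | 8–10% | 5–8% |

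**6. The alternatives.** The unweighted paired test stays at about 5% and 2.5% throughout. Weights 1/(tau² + SE_i²) with tau² estimated from the data also stay close to 5%, except about 5.5 to 7% in the extreme cases where fit error exceeds half the variance. With a 90% between-patient share and log-SD 0.35, power at a difference of 3.5 is 80.8% unweighted and 80.9% with these weights (tau² known).

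**The case against.** The strongest reply is that the decisive line cannot be read. Weights of 1/(tau² + SE²) would also give less influence to imprecise patients, as Step 3 asks, and would hold the nominal level closely. Redacted text is not missing text. This stands, and it makes the point conditional.

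Three stronger readings are tempting, and the documents support none of them.

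- That patients are weighted by fit error and nothing else. The visible text points that way, but the formula is hidden.
- That most of the 7-point SD lies between patients. The plan never splits it; step 2 of the working shows only that this is plausible.
- That the 5% and 2.5% levels are exceeded as a matter of course. The ingredient that the documents do give, the effect of where the best AV delay falls, yields only about 6% and 3%. The 2.4-fold ratio of fit variances (31/35 against 13/35) is an extreme, because a paired difference averages two of them. The larger figures need 1/SE² weights together with a wide, assumed spread of residual error.

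It can also be said that the study calls itself exploratory and leaves its ten planned comparisons unadjusted (SAP 7.5), so no study-wide error rate is claimed. That lowers the stakes. It does not excuse a single test or interval from the level that the SAP states for it.

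**Conclusion.** The concern holds as a conditional one. If the Step 4 weights rest on fit error alone and between-patient variance is material, the weighted test is anticonservative by an amount set by how unequal the weights are. The excess is slight when patients are measured with similar precision, and serious (three to four times the two-sided level) when residual error varies with log-SD 0.5 and the weights are 1/SE². It vanishes if the weights are equal, if tau² is nil, or if tau² is already in the weights.

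The figures assume normal differences, a patient effect unrelated to precision, fit SEs treated as known, and the standard weighted variance formula. Residual SD and its spread are assumptions, because neither document reports them.

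Separately, moving from the protocol's unweighted test to a weighted one is a change of method, which sits badly with the no-deviation statement in SAP 7.12.

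**What to change.** Make the unweighted paired t-test of protocol H.1.1 the primary analysis for Tables 9, 11, 12 and 13, and keep the weighted test as a sensitivity analysis with its weight formula written out. This also brings the analysis back in line with the sample size calculation.

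If weighting stays primary, use weights 1/(tau² + SE_i²). SE_i² is the squared fit standard error of the patient's paired difference, and tau² is estimated from the paired differences (their observed variance minus the mean SE_i², or REML). Table 8 reports single configurations, so there use that configuration's own SE² and its own tau². List the weighted test in SAP 7.12 as a change from the protocol.

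The cost is a sentence and a line of code, and a slightly larger reported SE: about 1.19 instead of 1.13 to 1.17 in the middle scenarios (log-SD 0.25 to 0.35, between-patient share 80 to 95%). Planned power is kept. If the existing formula already includes a between-patient term, the weights need no change; one sentence should say so.

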**Table 8: Percentage Change LV dP/dt max per configuration**

Comparison	Number of Subjects	Difference in % change LV dP/dt max	95 % Confidence interval
BiV basal	N	x.xx	x.xx – x.xx
BiV mid	N	x.xx	x.xx – x.xx
BiV apical	N	x.xx	x.xx – x.xx
MultiSpot SYN	N	x.xx	x.xx – x.xx
MultiSpot SEQ	N	x.xx	x.xx – x.xx

**Table 9: Results for Comparison MultiSpot SYN to BiV pacing**

Comparison	Number of Subjects	Difference in % change LV dP/dt max	95 % Confidence interval	P-value
MultiSpot SYN – BiV basal	N	x.xx	x.xx – x.xx	x.xxxx
MultiSpot SYN – BiV mid	N	x.xx	x.xx – x.xx	x.xxxx
MultiSpot SYN – BiV apical	N	x.xx	x.xx – x.xx	x.xxxx

The difference between optimal and best AV delay and the obtained % changes at these AV delays will be summarized in a table similar to the table below. Since the analysis methods for primary objective #1, #2 and secondary objective #1 are similar, the table will summarize results from all three objectives.

**Table 10: Difference between optimal AV delay and best AV delay**

	BiV basal (N =X)	BiV mid (N =X)	BiV distal (N =X)	MultiSpot SYN (N =X)	MultiSpot SEQ (N =X)
Difference between optimal AV delay and best AV delay					
Mean ± Standard Deviation	X ± Y	X ± Y	X ± Y	X ± Y	X ± Y
Median	X	X	X	X	X
25 th Percentile – 75 th Percentile	X – Y	X – Y	X – Y	X – Y	X – Y
Minimum – Maximum	X - Y	X - Y	X – Y	X - Y	X - Y
Number of Subjects With Measure Available (N,%)	X (Y%)	X (Y%)	X (Y%)	X (Y%)	X (Y%)
Difference between % change LV dP/dt max at optimal AV delay and at best AV delay					
Mean ± Standard Deviation	X ± Y	X ± Y	X ± Y	X ± Y	X ± Y
Median	X	X	X	X	X
25 th Percentile – 75 th Percentile	X – Y	X – Y	X – Y	X – Y	X – Y
Minimum – Maximum	X - Y	X - Y	X – Y	X - Y	X - Y
Number of Subjects With Measure Available (N,%)	X (Y%)	X (Y%)	X (Y%)	X (Y%)	X (Y%)

## B. Determination of Patients/Data for Analysis

The analysis will be performed on patients in the analysis cohort. Furthermore, it is necessary that patient have measurements during MultiSpot SYN pacing and during the respective BiV configuration used for comparison.

### 7.9.2. Primary Objective #2

Compare the hemodynamic response of a MultiSpot-SEQ Left Ventricular pacing configuration (sequential LV pacing) to a single spot LV pacing configuration in patients undergoing a research study, an EP exploratory procedure or CRT implant using the contractility parameter positive LV dP/dt max.

#### 7.9.2.1. Hypothesis

It is hypothesized that MultiSpot pacing sequentially (from apex to mid and then to base) is superior to BiV pacing. The null and alternative hypotheses are:

$$H_0: \Delta_{\text{MultiSpot SEQ}} - \Delta_{\text{BiV}} = 0\%$$

$$H_1: \Delta_{\text{MultiSpot SEQ}} - \Delta_{\text{BiV}} \neq 0\%,$$

where  $\Delta$  indicates percentage change from baseline for the respective pacing configuration.

Statistical analysis will use the methods described for the primary objective 1, with MultiSpot-SYN LV pacing replaced by MultiSpot-SEQ LV pacing configuration. The hypothesis will be assessed for the following three comparisons: MultiSpot SEQ to BiV basal (standard CRT), MultiSpot SEQ to BiV mid, and MultiSpot SEQ to BiV apical. In particular, the comparison of MultiSpot SEQ to standard CRT is of interest.

### 7.9.2.2. Endpoint Definition

The endpoint is the same as for the primary objective #1, i.e., % change LV dP/dt max from baseline (AAI pacing).

### 7.9.2.3. Analysis Methods

#### A. Statistical Methodology

Statistical analysis will use the methods described for the primary objective 1, with MultiSpot-SYN LV pacing replaced by MultiSpot-SEQ LV pacing configuration.

Results will be summarized in a table similar to the table below:

**Table 11: Results for Comparison MultiSpot SEQ to BiV pacing**

Comparison	Number of Subjects	Difference in % change LV dP/dt max	95 % Confidence interval	P-value
MultiSpot SEQ – BiV basal	N	x.xx	x.xx – x.xx	x.xxxx
MultiSpot SEQ – BiV mid	N	x.xx	x.xx – x.xx	x.xxxx
MultiSpot SEQ – BiV apical	N	x.xx	x.xx – x.xx	x.xxxx

